5.0 TREATMENT PROGRAM

5.1 Overview of Treatment Plan

Treatment Schedule Table	
Days 1-28	Vemurafenib 550 mg/m ² /dose BID (max: 960 mg PO BID)
Day 28	Evaluation

Vemurafenib will be given orally twice daily without regards to meals. Doses should be administered orally in the morning and evening. If vomiting occurs after a dose is taken, do not take an additional dose; continue with the next scheduled dose. Swallow whole with a glass of water; do not crush or chew. A missed dose can be taken up to 4 hours prior to the next dose.

A cycle of therapy is considered to be 28 days. A cycle may be repeated up to a total duration of therapy of approximately 2 years (maximum 26 cycles).

Patients will be treated at the established pediatric MTD/RP2D which is 550 mg/m²/dose BID (capped at the adult MTD of 960 mg/dose).

Drug doses should be adjusted based on the BSA calculated from height and weight measured within 7 days prior to the beginning of each cycle and according to the dosing nomogram in [Appendix IV](#).

Therapy will be discontinued if there is evidence of progressive disease or drug related dose-limiting toxicity that requires removal from therapy ([Section 6.0](#)). Therapy may otherwise continue for up to 2 years provided the patient meets the criteria for starting subsequent cycles ([Section 5.2](#)) and does not meet any of the criteria for removal from protocol therapy criteria ([Section 10.0](#)).

Vemurafenib is distributed by the Pharmaceutical Management Branch, CTEP, DCTD, NCI. **Do not use commercial supply for study purposes.**

5.1.1 [Therapy Delivery Map](#)

See [Appendix V](#) for APEC1621G Therapy Delivery Map

5.2 Criteria for Starting Subsequent Cycles

A cycle may be repeated every 28 days if the patient has at least stable disease and has again met laboratory parameters as defined in the eligibility section, [Section 4.0](#) and eligible to continue agent administration per the requirements in [Section 6.0](#).

5.3 Grading of Adverse Events

Adverse events (toxicities) will be graded according to the current version of the NCI Common Terminology Criteria for Adverse Events (CTCAE). All appropriate treatment areas should have access to a copy of the current version of the CTCAE version 5.0. A copy of the CTCAE version 5.0 can be downloaded from the CTEP website (<http://ctep.cancer.gov>). Any suspected or confirmed dose-limiting toxicity should be reported immediately (within 24 hours) to the Study Chair.

5.4 Definition of Dose-Limiting Toxicity (DLT)

DLT will be defined as any of the following events that are possibly, probably or definitely attributable to protocol therapy. Dose limiting hematological and non-hematological toxicities are defined differently.

5.4.1 Non-Hematological Dose-Limiting Toxicity

5.4.1.1 Any Grade 3 or greater non-hematological toxicity attributable to the investigational drug with the specific exclusion of:

- Grade 3 nausea and vomiting of less < 3 days duration
- Grade 3 liver enzyme elevation, including ALT/AST/GGT that returns to levels that meet initial eligibility criteria or baseline within 7 days See [Appendix XII](#) for values that represent thresholds between CTCAE grades.

Note: For the purposes of this study the ULN for ALT is defined as 45 U/L regardless of baseline.

- Grade 3 or 4 fever < 5 days duration.
- Grade 3 infection < 5 days duration.
- Grade 3 hypophosphatemia, hypokalemia, hypocalcemia or hypomagnesemia responsive to supplementation
- Grade 3 rash that is tolerable

- Any Grade 2 non-hematological toxicity that is considered sufficiently medically significant or sufficiently intolerable by patients that it requires treatment interruption
- Note: Allergic reactions that necessitate discontinuation of study drug will not be considered a dose-limiting toxicity.

5.4.2 Hematological dose limiting toxicity

5.4.2.1 Hematological dose limiting toxicity is defined as:

- a) In patients evaluable for hematological toxicity (see [Section 4.1.7.1](#)),
 - Grade 4 thrombocytopenia or neutropenia, not due to malignant infiltration.
 - Grade 3 thrombocytopenia that persists for ≥ 7 days
 - Grade 3 thrombocytopenia requiring a platelet transfusion on two

- separate days within a 7-day period
- Grade 3 thrombocytopenia with clinically significant bleeding
- Neutropenia or thrombocytopenia that causes a delay of > 14 days between treatment cycles (e.g. platelets <100K or ANC <1000)

5.4.2.2 Note: Grade 3 or 4 febrile neutropenia will not be considered a dose-limiting toxicity.

6.0 DOSE MODIFICATIONS FOR ADVERSE EVENTS

The Study Chair must be notified of any dosage modification or use of myeloid growth factor.

6.1 Dose Modifications for Hematological Toxicity

- 6.1.1 If a patient experiences hematological dose-limiting toxicity as defined in [Section 5.4.2.1](#), the treatment will be held. Counts should be checked every 3-4 days for thrombocytopenia and every other day for neutropenia during this time. If the toxicity resolves to meet eligibility parameters within 14 days of drug discontinuation, the patient may resume treatment at a reduced dose as outlined in the dose reduction guidelines (see [Appx IV-A](#) and [Appx IV-B](#)). Doses reduced for toxicity will not be re-escalated, even if there is minimal or no toxicity with the reduced dose.
- 6.1.2 If toxicity does not resolve to meet eligibility parameters within 14 days of drug discontinuation, the patient must be removed from protocol therapy.
- 6.1.3 Two dose reductions will be allowed for toxicity. If a patient experiences a hematological dose-limiting toxicity after two dose reductions, the patient must be removed from protocol therapy.

6.2 Dose Modifications for Non-Hematological Toxicity

- 6.2.1 If a patient experiences non-hematological dose-limiting toxicity as defined in [Section 5.4.1](#), the treatment will be held. When the toxicity resolves to meet eligibility parameters or baseline within 14 days of drug discontinuation, the patient may resume treatment at a reduced dose as outlined in the dose reduction table (see [Appx IV-A](#) and [Appx IV-B](#)). Doses reduced for toxicity will not be re-escalated, even if there is minimal or no toxicity with the reduced dose. See specific guidelines for QTc changes, severe hypersensitivity reactions, and dermatologic reactions below.
- 6.2.2 If toxicity does not resolve to meet eligibility or baseline parameters within 14 days of drug discontinuation, the patient must be removed from protocol therapy.
- 6.2.3 Two dose reductions will be allowed for toxicity. If a patient experiences dose-limiting toxicity after two dose reductions, the patient must be removed from protocol therapy.

6.3 Management/Dose Modification for QTc Prolongation

- 6.3.1 Avoid combination with other drugs with potential to lead to prolongation of QTc interval, if possible (See [Appendix VIII](#)).
- 6.3.2 ECG monitored prior to therapy and then monthly x 3 cycles and then every 3rd cycle ([Section 8.1](#))
- 6.3.3 See table below for dose modifications based on prolongation of the QTc interval:

Dose modification schedule based on prolongation of the QTc interval	Recommended dose modification
QTc increase meets values of both > 500msec and > 60 msec change from pre-treatment value	
• Discontinue permanently
1st occurrence of QTc > 500 msec during treatment and change from pre-treatment value remains < 60 msec	
• Interrupt treatment• Monitor Electrolytes and any electrolyte abnormality should be corrected• Monitor ECG weekly until QTc decreases to \leq 500 msec• Reinstitute therapy at reduced dose level -1 (or dose level -2 if patient has already had dose lowered) (see Appx IV-A and Appx IV-B)
2nd occurrence of QTc > 500 msec during treatment and change from pre-treatment value remains < 60msec	
• Interrupt treatment• Monitor Electrolytes and any electrolyte abnormality should be corrected• Monitor ECG weekly until QTc decreases to \leq 500 msec• Reinstitute therapy at reduced dose level -2 (or discontinue if patient already has already been lowered to dose level -2) (see Appx IV-A and Appx IV-B)
3rd occurrence of QTc > 500 msec during treatment and change from pre-treatment value remains < 60msec	
• Discontinue permanently

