	Constipation		Constipation (Gr 2)
	Diarrhea		Diarrhea (Gr 2)
Nausea		Pancreatitis	Nausea (Gr 2)
			Pancreatitis
	Vomiting		Vomiting (Gr 2)
GENERAL DISORDERS AND ADMINISTRATION SITE CONDITIONS			
	Edema limbs		Edema limbs (Gr 2)
Fatigue			Fatigue (Gr 2)
	Fever		Fever (Gr 2)
HEPATOBILIARY DISORDERS		Hepatic failure	
IMMUNE SYSTEM DISORDERS			
	Allergic reaction*		
		Anaphylaxis	

Adverse Events with Possible Relationship to Vemurafenib (Zelboraf, RO5185426) (CTCAE 5.0 Term) [n= 5019]			Specific Protocol Exceptions to Expedited Reporting (SPEER)
Likely (>20%)	Less Likely (<=20%)	Rare but Serious (<3%)	
INFECTIONS AND INFESTATIONS			
	Folliculitis		
	Infections and infestations - Other (nasopharyngitis)		
INJURY, POISONING AND PROCEDURAL COMPLICATIONS			
		Injury, poisoning and procedural complications - Other (radiation injury) ²	
INVESTIGATIONS			
	Alanine aminotransferase increased		Alanine aminotransferase increased (Gr 2)
	Alkaline phosphatase increased		Alkaline phosphatase increased (Gr 2)
	Aspartate aminotransferase increased		Aspartate aminotransferase increased (Gr 2)
	Blood bilirubin increased		
	Creatinine increased		Creatinine increased (Gr 2)
	Electrocardiogram QT corrected interval prolonged		Electrocardiogram QT corrected interval prolonged (Gr 2)
	GGT increased		GGT increased (Gr 2)
	Neutrophil count decreased*		Neutrophil count decreased* (Gr 2)
	Serum amylase increased*		Serum amylase increased* (Gr 2)
	Weight loss		Weight loss (Gr 2)
METABOLISM AND NUTRITION DISORDERS			
	Anorexia		Anorexia (Gr 2)
MUSCULOSKELETAL AND CONNECTIVE TISSUE DISORDERS			
Arthralgia			Arthralgia (Gr 2)
	Back pain		Back pain (Gr 2)
	Musculoskeletal and connective tissue disorder - Other (Dupuytren's contracture and plantar fibromatosis)*		
	Myalgia		Myalgia (Gr 2)
	Pain in extremity		Pain in extremity (Gr 2)
NEOPLASMS BENIGN, MALIGNANT AND UNSPECIFIED (INCL CYSTS AND POLYPS)			
	Skin papilloma		Skin papilloma (Gr 2)
	Treatment related secondary malignancy - Cutaneous squamous cell carcinoma (SCC), including keratocanthoma or mixed keratocanthoma subtype		
		Treatment related secondary malignancy - including non-cutaneous squamous cell carcinoma, melanoma and others	
		Treatment related secondary malignancy - progression of RAS mutant tumors	
NERVOUS SYSTEM DISORDERS			
	Dizziness		Dizziness (Gr 2)

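### The first-occurrence QTc row in 6.3.3 has no discontinue option for an Appendix IV-B patient already at dose level -2

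*Combined protocol and SAP*

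**What the plan says.** Section 6.3.3 sets the action for QTc prolongation in a table whose action column is headed "Recommended dose modification". For a first QTc above 500 msec with a change below 60 msec, treatment is interrupted, electrolytes are corrected and the ECG is repeated weekly until QTc is 500 msec or less. Then: "Reinstitute therapy at reduced dose level -1 (or dose level -2 if patient has already had dose lowered"). The second-occurrence row restarts at level -2 but discontinues a patient who is already there. A third occurrence stops treatment permanently.

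The general rule for non-hematological toxicity is in 6.2. Section 6.2.3 allows two reductions and then states: "If a patient experiences dose-limiting toxicity after two dose reductions, the patient must be removed from protocol therapy". Section 6.2.1 says "Doses reduced for toxicity will not be re-escalated, even if there is minimal or no toxicity with the reduced dose", and adds: "See specific guidelines for QTc changes, severe hypersensitivity reactions, and dermatologic reactions below".

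DLT status comes from 5.4 ("DLT will be defined as any of the following events that are possibly, probably or definitely attributable to protocol therapy") and 5.4.1, which covers attributable non-hematological toxicity of Grade 3 or higher, with listed exclusions. QTc prolongation is not among the exclusions. One bullet in the same list reads: "Any Grade 2 non-hematological toxicity that is considered sufficiently medically significant or sufficiently intolerable by patients that it requires treatment interruption". The adverse event table in 9.1.4 lists "Electrocardiogram QT corrected interval prolonged" as an event with a possible relationship to vemurafenib.

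Appendix IV-B gives a treatment dose at level -2 in all three BSA bands. In Appendix IV-A (BSA 0.55 to 0.72 m²), level -2 means coming off protocol treatment.

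**The concern.** The first-occurrence row has one branch for any patient whose dose has been lowered before, and that branch leads to level -2. It does not separate a patient at level -1, for whom level -2 is a further reduction, from a patient already at level -2, for whom it is no change. For the second patient the row gives a restart at the same dose after QTc exceeded 500 msec, although no lower dose exists.

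A site managing a QTc event will turn to the QTc table, because 6.2.1 sends it there. If the event is also a DLT, 6.2.3 calls for removal, and the protocol does not say which section prevails. If the event is not judged a DLT, 6.2.3 does not apply and the table is the only specific dosing rule. At stake is one cardiac-safety dosing decision for an unusual patient. No statistical property of the design is involved.

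**Working it through.** No plan figure needs reproducing. The check traces the 6.3.3 table through the nomograms and compares the result with 6.2.3.

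**Step 1: can the state be reached?** Two reductions are allowed (6.1.3, 6.2.3), and reduced doses are not raised again (6.1.1, 6.2.1). An Appendix IV-B patient reduced twice for other toxicity therefore stays at level -2 and may then have a first QTc event.

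**Step 2: trace the table, change below 60 msec.**

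| Nomogram | Level at event | First-occurrence row | Second-occurrence row |
|---|---|---|---|
| IV-B | 0 | restart at -1 | cannot arise (no re-escalation) |
| IV-B | -1 | restart at -2 | restart at -2 |
| IV-B | -2 | restart at -2, **no change** | discontinue |
| IV-A | 0 | restart at -1 | cannot arise |
| IV-A | -1 | level -2, i.e. off treatment | level -2, i.e. off treatment |

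The only unresolved entry is a first occurrence under IV-B at level -2. Appendix IV-A has no gap, because its level -2 is itself removal.

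**Step 3: dose involved (total mg per day, from Appendix IV-B).**

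| BSA (m²) | Start | Level -1 | Level -2 |
|---|---|---|---|
| 0.73–1.09 | 480 + 480 = 960 | 240 + 480 = 720 | 240 + 240 = 480 |
| 1.1–1.53 | 720 + 720 = 1440 | 480 + 480 = 960 | 240 + 480 = 720 |
| ≥ 1.54 | 960 + 960 = 1920 | 720 + 720 = 1440 | 480 + 480 = 960 |

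Level -2 is 480/960 = 720/1440 = 960/1920 = 50% of the starting dose. The row adds no further reduction.

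**Step 4: who can meet the row's QTc condition?** The row needs on-treatment QTc > 500 and (on-treatment − pre-treatment) < 60. Hence pre-treatment QTc > 500 − 60 = 440 msec. Section 4.1.7.4 caps QTc at 480 msec for eligibility. Taking the eligibility value as the pre-treatment value, the range is above 440 and at most 480 msec. At 440 or below, any QTc above 500 is a rise of more than 60 and falls in the permanent-discontinuation row.

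**Step 5: compare with 6.2.3.**
- *Event is a DLT:* 6.2.3 says remove; the first-occurrence row says restart. They conflict.
- *Event is not a DLT:* 6.2.3 is silent, and the row alone applies.

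Which case holds cannot be decided from the documents. They give no CTCAE cut-offs for QTc; Appendix XII covers bilirubin, ALT, AST and GGT only. The Grade 2 interruption bullet is printed inside the 5.4.1.1 exclusion list, so treating it as a DLT trigger is an interpretation. In favour of DLT status, possible attribution is enough, QTc prolongation is a listed event, and the row itself orders interruption.

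**Step 6: the 60 msec boundary.** The permanent-discontinuation row needs a change above 60 msec and the other rows need one below 60. A change of exactly 60 msec with QTc above 500 falls in no row. If such an event is a DLT, 6.2.1 still holds the drug.

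**The case against.** The strongest reply is that the important case is already controlled. Section 6.2.3 is mandatory and has no QTc exception, whereas the QTc column is only a recommendation. The pointer to the QTc guidelines sits in 6.2.1, not 6.2.3. A suspected DLT goes to the Study Chair within 24 hours (5.3), dose modifications are notified (6.0), evaluations are reviewed weekly (14.4.2), a DLT must resolve within 14 days (6.2.2), and the physician may stop treatment at any time (10.1). A site reading all of Section 6 would remove a patient whose event is a DLT. This stands, and it limits the practical risk. It does not make the row correct: the table still gives a different action, no precedence is stated, and 6.2.3 says nothing about events not judged DLTs.

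A second reply is that restarting at level -2 after a first event may have been intended, with a stricter step at the second. The documents do not exclude that. The word for a lowered dose could mean only lower than the starting dose, and a second event may reasonably be treated more severely. The discontinue branch in the adjacent row and Appendix IV-A's treatment of level -2 make an oversight more likely but do not prove one.

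A reader might infer something stronger: that the protocol plainly orders re-treatment of a patient whom it elsewhere requires to be removed. The documents do not support that as a general statement, because the contradiction exists only when the event is a DLT and its grade cannot be fixed from the text. Nor do they support reading the 60 msec gap as a material hazard. It concerns a single value, and 6.2.1 still applies to a DLT.

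**Conclusion.** The point holds as a minor patient-safety wording error. For an Appendix IV-B patient already at level -2, the first-occurrence row, read literally, restarts treatment at an unchanged dose. That conflicts with 6.2.3 whenever the event is a DLT, and it differs from the second-occurrence row in every case.

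The case is rare. It requires BSA of at least 0.73 m², two earlier reductions, a pre-treatment QTc above 440 and at most 480 msec, and a first event with a change below 60 msec, among at most 49 patients. The documents give no frequency for this combination, so none is offered. The literal consequence is bounded, because a second occurrence at level -2 stops treatment.

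The conclusion rests on a literal reading of the row and on the pre-treatment QTc meeting the eligibility cap. The conflict with 6.2.3 also rests on the event being a DLT; the missing option does not. The change should be made at the next amendment.

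**What to change.** Replace the restart instruction in the first-occurrence row with three explicit branches, for example: *restart at dose level -1; if the event occurred at dose level -1, restart at dose level -2; if it occurred at dose level -2, discontinue.* This agrees with 6.2.3 when the event is a DLT, gives one clear action when it is not, and matches the second-occurrence row at level -2.

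Optional tidy-up: assign a change of exactly 60 msec to one row, by writing either ≥ 60 in the permanent-discontinuation row or ≤ 60 in the others. The first stops such a patient permanently and the second allows a restart. The documents do not favour either, so the choice is the sponsor's.

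The cost is one or two wording edits to one table. Sample size, visits, data collection and analysis do not change.

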6.4 Management for cutaneous squamous cell carcinoma

- 6.4.1 A complete dermatological history of prior medications and cutaneous squamous cell carcinoma (cuSCC) risk factors (i.e. radiation therapy, sun exposure, immunosuppression, prior SCC, use of tanning beds, precursor lesions, photo chemotherapy) must be collected.
- 6.4.2 A dermatologist will perform regular skin exams to monitor for cuSCC, BCC, actinic keratosis, keratoacanthoma, and second primary melanomas. Any suspicious lesion should be mapped and photographed, and must be definitively treated (i.e. full surgical excision) and sent for pathological examination (shaved biopsies are not recommended).
- 6.4.3 Dermatology examinations will occur at baseline prior to starting drug, prior to

every cycle x 3, and then every 3 cycles while on therapy treatment, and continue for 30 days after last study treatment or until death, withdrawal of consent or lost to follow up, whichever is earlier.

- 6.4.4 Actinic keratosis, keratoacanthoma or other skin conditions identified by the dermatologist should be treated as per local standard of care.
- 6.4.5 Treatment interruption or dose modification is not required for occurrence of cuSCC.

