6.7 Management/dose modifications for dermatologic reactions

- 6.7.1 Severe dermatologic reactions have been reported in patients receiving vemurafenib, including rare cases of Stevens-Johnson Syndrome and toxic epidermal necrolysis in the pivotal clinical trial. Drug reaction with eosinophilia and systemic symptoms syndrome (DRESS) has been reported in association with vemurafenib. In patients who experience a severe dermatologic reaction, vemurafenib should be permanently discontinued.
- 6.7.2 Patients who experience Grade \leq 3 photosensitivity/rash should be managed with supportive care. For intolerable Grade 2 or Grade \geq 3 photosensitivity, vemurafenib should be held until resolution to Grade \leq 1 and managed with dose modification per [Section 6.2](#).

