6.8 Management of liver injury

- 6.8.1 Liver injury, including severe cases of liver injury has been reported with vemurafenib. Liver enzymes (transaminases and alkaline phosphatases) and bilirubin should be measured as per [Section 8.1](#). Laboratory abnormalities should be managed with dose modification per [Section 6.2](#).

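### For Grade 3 or higher cuSCC attributed to vemurafenib, Section 6.2.1 calls for a hold and a reduced dose while Section 6.4.5 requires neither, and the protocol does not say which governs dosing

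*Combined protocol and SAP*

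**What the plan says.** **DLT definition.** Section 5.4 sets a low bar for attribution: "DLT will be defined as any of the following events that are possibly, probably or definitely attributable to protocol therapy". Section 5.4.1.1 then counts "Any Grade 3 or greater non-hematological toxicity attributable to the investigational drug with the specific exclusion of" a list of named events. These are short-lived nausea and vomiting, reversible liver enzyme rises, short fever, short infection, correctable electrolyte changes and tolerable rash. A note adds that allergic reactions leading to discontinuation are not DLTs. Neither cuSCC nor secondary malignancy is listed.

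**Consequence of a DLT.** Under Section 6.2.1, treatment is held. If the toxicity resolves within 14 days, the patient may restart at a reduced dose, and "Doses reduced for toxicity will not be re-escalated, even if there is minimal or no toxicity with the reduced dose". Section 6.2.2 requires removal from protocol therapy if it does not resolve in that time. Section 6.2.3 allows two reductions. Section 6.2.1 ends with a pointer: "See specific guidelines for QTc changes, severe hypersensitivity reactions, and dermatologic reactions below".

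**cuSCC rule.** Section 6.4.2 requires definitive treatment of suspicious lesions, such as full excision. Section 6.4.4 adds: "Actinic keratosis, keratoacanthoma or other skin conditions identified by the dermatologist should be treated as per local standard of care". Section 6.4.5 closes: "Treatment interruption or dose modification is not required for occurrence of cuSCC".

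**The concern.** For one foreseeable event, a mandatory hold and a statement that no hold is required give a site two different instructions.

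The event is foreseeable on the protocol's own terms. The adverse event list in Section 9.1.4 shows cuSCC as possibly related to vemurafenib. Section 13.3 exempts only Grade 1 and 2 cuSCC from expedited reporting, which presumes that higher grades can occur.

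A site that follows 6.2.1 to the letter would interrupt treatment and permanently lower a child's dose for a lesion that 6.4.5 says needs neither. That would also use up one of the allowed reductions. Section 2.3.1 reports that in the adult phase 1 study most such lesions were resected without the drug being stopped.

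**Working it through.** The plan gives no figure to reproduce here. The check is a trace of the rules, followed by the dose arithmetic.

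**Trace for an attributable Grade 3 or higher cuSCC**

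| Step | DLT route | cuSCC section |
|---|---|---|
| Is it a DLT? | Yes: attributable, Grade 3 or higher, not excluded (5.4, 5.4.1.1) | Not addressed |
| Hold treatment? | Yes (6.2.1) | Not required (6.4.5) |
| Dose on resuming | Reduced, no re-escalation (6.2.1) | No change required (6.4.5) |
| Unresolved at 14 days | Removal (6.2.2) | Not addressed |

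The routes diverge on dosing. They do not diverge on whether a DLT occurred, because 6.4.5 is silent on that.

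**Does the pointer in 6.2.1 settle it?** It names three topics: QTc changes, severe hypersensitivity and dermatologic reactions. These match the three later sections whose titles mention dose modification: 6.3, 6.6 and 6.7. Section 6.7 covers Stevens-Johnson syndrome, toxic epidermal necrolysis, DRESS, photosensitivity and rash. It does not mention cuSCC, so the pointer does not clearly reach 6.4.

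**Does the layout of Section 6 settle it?** It indicates intent. Where the drafters wanted 6.2 applied, they said so. Section 6.7.2 says that for intolerable or severe photosensitivity "vemurafenib should be held until resolution to Grade" 1 or lower, then refers to 6.2. Section 6.8.1 says "Laboratory abnormalities should be managed with dose modification per" Section 6.2, and 6.9.1 does the same for eye events. Section 6.4 makes no such reference and states its own dosing rule. That favors 6.4.5, but by inference only.

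**Size per patient.** Inputs are the assigned dose and dose level -1 in Appendices IV-A and IV-B. Change = (level -1 daily dose - assigned daily dose) / assigned daily dose.

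| BSA (m²) | Assigned (mg/day) | Level -1 (mg/day) | Change |
|---|---|---|---|
| 0.55-0.72 | 240 + 480 = 720 | 2 × 240 = 480 | -240/720 = -33% |
| 0.73-1.09 | 2 × 480 = 960 | 240 + 480 = 720 | -240/960 = -25% |
| 1.1-1.53 | 2 × 720 = 1440 | 2 × 480 = 960 | -480/1440 = -33% |
| 1.54 and above | 2 × 960 = 1920 | 2 × 720 = 1440 | -480/1920 = -25% |

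Under 6.4.5 the change is 0% in every band. For BSA 0.55-0.72 m², level -2 is removal from protocol therapy, so on the DLT route a second such event ends treatment.

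**Frequency.** Section 9.1.4 (5019 patients) puts cuSCC, grouped with keratoacanthoma, in the column for events at 20% or less, without the asterisk that marks events below 3%. That bounds the any-grade rate at about 3% to 20%. No Grade 3 or higher share and no age breakdown is given, so the number of children affected cannot be derived.

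**The case against.** The strongest reply is that the protocol already answers the question. Section 6 sets a default in 6.2, and event-specific sections then depart from it. Section 6.4.5 is event-specific and speaks directly to interruption and dose change, so its evident job is to displace the default. Any change of dose must be notified to the Study Chair (Section 6.0), and study leadership reviews data weekly (14.4.2), so a single case can be resolved. This stands as a reading of intent, and it is why the severity is low. It does not remove the conflict. Elsewhere the drafters wrote exceptions out: allergic reactions in 5.4.1.1 and febrile neutropenia in 5.4.2.2 are expressly not DLTs. A reader could also reconcile the two rules the other way, taking 6.4.5 to mean that a lesion's mere occurrence needs no action while a Grade 3 lesion does.

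Four stronger readings are tempting but not supported:

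- *The DLT definition is wrong, or DLT recording is inconsistent.* Section 6.4.5 concerns dosing only. A Grade 3 or higher cuSCC can be recorded as a DLT and still need no dose change. Excluding cuSCC from 5.4.1.1 would also end the 24-hour DLT report to the Study Chair under Section 5.3, including for Grade 4 events.
- *A dose reduction is mandatory.* Section 6.2.1 makes it a condition of resuming; the alternative is to stay off drug or be removed.
- *Keratoacanthoma should be left out because 6.4.4 handles it.* Section 6.4.4 governs treatment of the lesion, not vemurafenib dosing, and 4.2.3 counts keratoacanthoma and the mixed subtype as cuSCC.
- *The efficacy result is at risk.* The rule of at least 3 responses in 20 (11.3.1) and evaluability after one dose (11.5) do not depend on which dosing rule is followed, and no frequency is available to support a claim about diluted response.

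**Conclusion.** The conflict is real but narrow. It applies when cuSCC is Grade 3 or higher and attributed to vemurafenib. In that case the literal DLT route imposes a hold and, for a patient who continues, a daily dose 25% or 33% lower that is not raised again, or removal if the event is unresolved at 14 days. Section 6.4.5 requires none of this, and precedence is not stated.

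The conclusion rests on two readings: that the exclusion list in 5.4.1.1 is complete as written, and that the reference to dermatologic reactions in 6.2.1 means Section 6.7. Both follow from the text. That 6.4.5 is meant to govern is an inference from layout.

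The effect is confined to individual dosing. The DLT definition, DLT recording, the toxicity tables, the response-rate decision rule and the sample size are unaffected. How many children it would reach is unknown. This is a low-severity correction.

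**What to change.** At the end of 6.2.1, add to the list of specific guidelines: *cutaneous squamous cell carcinoma (Section 6.4, which governs dosing for this event)*. State that cuSCC has the meaning in 4.2.3, including keratoacanthoma and the mixed subtype, so that the ambiguity does not simply move to those lesions.

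Leave 5.4.1.1 unchanged, so that Grade 3 or higher cuSCC is still recorded and reported as a DLT.

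The cost is one added term and a cross-reference to an existing definition. No visit, procedure or data item is added. Because the precedence is inferred, the study chair should confirm the intent when the wording is amended.
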